6.4 Sample Size and Power

Assuming 100% capture of eligible patients (waivers of consent obtained from all participating sites), we expect to identify a total of 600 newly diagnosed AML/MDS patients across the seventeen participating centers. Assuming 90% of identified patients will be early discharge eligible, the anticipated study population will be 540 patients. Based on the rates for the individual participating sites, approximately 27% of the study population will be managed as outpatients (n=146) and the remaining will be managed as inpatients (n=394) during neutropenia. Assuming a baseline risk of bacteremia of 60%, the proposed size of the two study arms would provide greater than 80% power to detect a 13% difference in bacteremia rates among patients managed as outpatients versus those that remain hospitalized, with a significance level of 0.05. A 13% difference in bacteremia rates would also be a clinically significant difference. For time to next chemotherapy course, we used a two sample t-test in the power calculation to be conservative (i.e., statistical analysis using a generalized linear model with correct distribution will result in creased power over a t-test). Assuming each patient contributes one treatment course and an average time to next chemotherapy course of 29 days and a standard deviation (SD) of 10 (based on preliminary data), our study will have 85.0% power to detect a difference of 3 days between the two groups, with a significance level of 0.05.

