1 BACKGROUND INFORMATION AND RATIONALE

1.1 Introduction

Acute myeloid leukemia (AML) is the second most common pediatric hematologic malignancy with approximately 600 new cases per year among patients under 20 years of age. Although AML accounts for only about 20% of leukemias in children, it is responsible for more than half of pediatric leukemia deaths (1).

All pediatric patients with newly diagnosed AML receive multiple consecutive courses of intensive myelosuppressive chemotherapy aimed to attain complete remission (induction) and to prevent relapse (intensification) (2). Each regimen is followed by a period of prolonged severe neutropenia during which patients are at high risk for infection and hemorrhage. Previous reports have found that 57-80% of febrile neutropenia episodes among pediatric AML patients are compromised by at least one microbiologically documented infection (3, 4) with bacteremia constituting the most prevalent infection (5). These infectious complications remain a major cause of therapy-associated morbidity and mortality in children with AML (6, 7).

Recently published pediatric neutropenia guidelines make no specific recommendations regarding discharge from hospital after chemotherapy for AML because "there are no validated schemas for defining those patients at high-risk of developing complications of fever and neutropenia" (8). As a result, clinicians are left to decide whether to keep a child in the hospital until the neutropenia resolves (on average 35 days) or discharge a child to outpatient management within a few days of chemotherapy completion with instructions to return if symptoms of infection develop. Physicians that elect to observe patients with neutropenia in the hospital do so under the assumption that hospital observation will reduce the risk of serious infection and thereby reduce delays in starting the next course of chemotherapy. There is documented variation in practice across Children's Oncology Group (COG) institutions on inpatient versus outpatient management of neutropenia with approximately 60% of COG institutions reporting a policy to always keep patients hospitalized during severely neutropenic periods and the remaining 40% of hospitals reporting a policy of home management some or all of the time (9, 10). This variation in practice highlights the need for additional data on clinician-centered outcomes to appropriately guide the management of neutropenia in pediatric AML patients.

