1.2 Relevant Literature and Data

The limited literature on the clinical consequences of outpatient versus inpatient management of neutropenia in AML is focused on the experience of adult patients. Adult

patients discharged early to outpatient supportive care consistently had shorter cumulative lengths of stay than inpatients (11-18). Additionally, early discharge of adult AML patients receiving chemotherapy has been associated with fewer and shorter febrile episodes (15, 19), a better response to first line antibiotics, and shorter duration of intravenous antibiotic administration (13, 15, 18, 19). While these adult studies provide some reassurance that outpatient management may be safe and feasible they are limited as most included data from only a single institution, had very small sample sizes, or lacked an appropriate inpatient reference population. Furthermore, it is not appropriate to extrapolate these adult findings to pediatric patients as the risk profile for children may be much different.

The published literature with respect to outpatient management of neutropenia in pediatric AML is limited to a single study of only 13 patients from one hospital, which found similar rates of relapse and mortality for outpatient versus inpatient management of neutropenia (20). In our own preliminary analyses based on administrative resource utilization data from 43 free-standing children's hospitals in the US, we found that patients who were discharged early to outpatient management following AML induction and intensification chemotherapy courses incurred fewer cumulative days of hospitalization, but were frequently readmitted and had higher rates of antibiotic, vasopressor, and supplemental oxygen utilization than patients who remained inpatient during the entirety of their neutropenia. In the absence of clinical data and laboratory confirmation, it is unclear whether these observed increases in resource utilization are an accurate proxy for a greater incidence of infection or more severe infection in the early discharge patients.

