2.1 Primary Objectives

- **2.1.1** Compare the incidence of bacteremia among children with AML or MDS receiving standard intensive AML frontline chemotherapy monitored in the outpatient setting during neutropenia ("early discharge") relative to those who remain hospitalized ("inpatient").
- **2.1.2** Compare the length of time to initiation of the subsequent chemotherapy course between children with AML or MDS receiving standard intensive AML frontline chemotherapy monitored in the outpatient setting during neutropenia to similar children who remain hospitalized.

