6.3 Statistical Methods

6.3.1 Analysis of Primary Outcomes of Interest

Propensity score analyses will be used to adjust for potential confounding by baseline covariates. First, bivariate analyses will be performed to evaluate relationships between each baseline covariate and neutropenia management strategy as well as each outcome of interest. Next, propensity scores will be derived from the predicted probabilities estimated from logistic regression models of the use of outpatient versus inpatient management during neutropenia conditional on all baseline factors determined to be true confounders (i.e., those associated with both exposure and outcome) and those determined to be potential confounders (i.e., those associated only with the outcome interests). Patients will then be stratified into five groups using quintiles of the estimated propensity score. The distributions of exposure within the quintiles will be examined for sufficient sample sizes and balance. Within each stratum, the patients managed as outpatient and those managed as inpatient will ideally have similar values of the propensity score and likewise the distribution of measured baseline covariates will be comparable between them.

Log-binomial regression will be used to estimate risk ratios with 95% confidence intervals (CI) comparing the incidence of bacteremia following outpatient versus inpatient neutropenia management strategy. Control for confounding will be accomplished through adjustment for propensity score by quintiles as well as any remaining unbalanced patient- or hospital-level confounders.

Generalized linear regression models will be utilized to compare time (in days) from three days after completion of one chemotherapy course to initiation of the next course of chemotherapy by neutropenia management strategy (outpatient versus inpatient). Before model fitting, the normality of the outcome will be assessed. If the normality assumption holds, then traditional linear models (normal distribution with an identity link) will be utilized. If the distribution of time to next course is significantly skewed, then models assuming a gamma or log-normal distribution as appropriate will be used. Again, control for confounding will be accomplished through adjustment for propensity score by quintiles as well as any remaining unbalanced confounders.

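### Section 6.4 claims more than 80% power for a 13-point bacteremia difference in either direction, but on a two-sided test this holds only for an increase (about 81%, against 77% for a decrease); the 85.0% for time to next course does not follow from the printed inputs (87.1%)

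*Combined protocol and SAP*

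**What the plan says.** All of the power statements are in section 6.4 (Sample Size and Power). From 600 identified patients, 90% early-discharge eligible, the plan expects 540, split 146 outpatient (27%) and 394 inpatient.

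- **Bacteremia.** "Assuming a baseline risk of bacteremia of 60"%, the section claims "greater than 80% power to detect a 13% difference in bacteremia rates among patients managed as outpatients versus those that remain hospitalized" at a significance level of 0.05. It adds that a 13% difference would be clinically significant. It does not say whether the difference is an increase or a decrease, or whether the 0.05 is one- or two-sided.
- **Time to next course.** With a two-sample t-test, a mean of 29 days, an SD of 10 and one course per patient, "our study will have 85.0% power to detect a difference of 3 days between the two groups", again at 0.05.

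Two other sections bear on how the bacteremia sentence is read. Objective 2.1.1 is non-directional: "Compare the incidence of bacteremia among children with AML or MDS", outpatients relative to those who stay in hospital. Section 6.3.1 plans the matching estimate: "Log-binomial regression will be used to estimate risk ratios with 95% confidence intervals (CI").

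**The concern.** Around a 60% baseline, a 13-point change does not have the same power in both directions. Moving down to 47% brings the rate closer to one half, where binomial variance is largest. Moving up to 73% takes it away from one half. When the calculation sits just above 80% in one direction, it can fall below 80% in the other.

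The objective asks which strategy does better without presuming the answer, and the plan calls 13% clinically significant without a sign. A reader will therefore take the 80% as covering a reduction as well. What is at stake is how a null result is read: someone judging it against the planned power would credit the study with slightly more ability to detect a benefit of outpatient management than it has.

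The 85.0% raises a different question. It is printed to one decimal, with its test, SD, difference, level and arm sizes, so it should be recoverable from them.

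**Working it through.** **Inputs, all from section 6.4.** Outpatients n_O = 146, inpatients n_I = 394, baseline 60%, difference 13 percentage points, level 0.05; for time, difference 3 days and SD 10. The arm sizes reproduce: 600 × 0.90 = 540, 540 × 0.27 = 145.8, and 540 − 146 = 394.

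**Readings adopted.** The 60% is the inpatient rate, because objective 2.1.1 and sections 6.3.1 and 6.4 all set outpatients against inpatients. The test is two-sided, because the objective is non-directional and 95% intervals are planned. The 13% is in points: read as a relative change it would give only about 37–38% power, so points must be meant.

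**Bacteremia, pooled two-proportion test, unadjusted.** With p̄ = (146·p_O + 394·p_I)/540,

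- SE0 = √[p̄(1−p̄)(1/146 + 1/394)]
- SE1 = √[p_O(1−p_O)/146 + p_I(1−p_I)/394]
- power = Φ[(|p_O − p_I| − 1.960·SE0)/SE1]

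*The plan's figure, as an increase (60% to 73%).* p̄ = 0.6351, SE0 = 0.04664, SE1 = 0.04426. Power = Φ[(0.13 − 0.09141)/0.04426] = Φ(0.872) = **80.8%**. The claim of more than 80% reproduces.

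*The same size of difference as a decrease (60% to 47%).* p̄ = 0.5649, SE0 = 0.04804, SE1 = 0.04812. Power = Φ[(0.13 − 0.09415)/0.04812] = Φ(0.745) = **77.2%**. The claim does not reproduce.

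Solving the same formula for 80% power gives +12.9 points or −13.5 points.

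**Sensitivity (394/146, 13 points, 60% inpatient).**

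| Test | Increase to 73% | Decrease to 47% |
|---|---|---|
| Pooled z, two-sided | 80.8% | 77.2% |
| Exact enumeration of Pearson chi-square, two-sided | 81.0% | 77.2% |
| Unpooled z, two-sided | 83.6% | 77.1% |
| Wald on log risk ratio, two-sided | 85.5% | 71.1% |
| Fisher exact, two-sided | 79.6% | 75.1% |
| Continuity-corrected z, two-sided | 77.8% | 74.1% |
| Pooled z, one-sided 0.05 | 88.6% | 85.5% |

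No two-sided version tried reaches 80% for the decrease. The increase passes with the ordinary uncorrected tests and falls just short with the two conservative ones. Placing the 60% in the outpatient arm instead does not rescue a claim for both directions: the pooled test gives 82.1% with outpatients lower (60% against 73%) and 76.9% with outpatients higher (60% against 47%).

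**Time to next course, two-sample t-test.** Noncentrality = 3/[10·√(1/146 + 1/394)] = 3/0.9689 = 3.096; df = 538; two-sided critical value 1.964. Power = **87.1%**. A one-sided test gives 92.6%, so neither sidedness returns 85.0%. An SD of 10.3, which would print as 10, gives 85.1%; a 135/405 split gives 85.4%. Neither of these inputs is in the documents.

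**The case against.** The strongest reply is that the bacteremia figure is right for the direction the authors probably had in mind. It reproduces at 80.8% for an increase. Section 1.1 reports the clinicians' assumption that "hospital observation will reduce the risk of serious infection", and the sponsor's 43-hospital data in section 1.2 found that early-discharge patients "had higher rates of antibiotic, vasopressor, and supplemental oxygen utilization". Both point towards more infection in outpatients. The opposite signal, that "early discharge of adult AML patients receiving chemotherapy has been associated with fewer and shorter febrile episodes", comes from adults, and section 1.2 itself says such findings should not be carried over to children. This stands as far as it goes: the adult data are no basis for expecting a decrease. But section 1.2 also calls the resource-use data an unclear proxy for infection, and neither the objective nor section 6.4 limits the comparison to an increase.

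A second reply is that a one-sided 0.05 test would make the sentence true both ways. That is correct arithmetically, but the documents state no one-sided test, and the non-directional objective with 95% intervals points to a two-sided one.

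A third is that the 85.0% may have been computed from unrounded inputs. This stands. The outpatient share is given as approximate and the SD comes from preliminary data, so the figure cannot be called wrong, only untraceable from what is printed.

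A fourth is that little depends on any of this: every eligible patient at the seventeen sites is to be included, and the confidence interval will show directly what a null result excludes. This also stands, and it is why the point is minor.

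**Conclusion.** The point holds and is minor. As worded, the bacteremia claim covers both directions, but the design delivers it in only one: about 81% for an increase to 73%, about 77% for a decrease to 47%. The shortfall for a decrease is about 3 points of power, or half a percentage point of detectable difference (13.5 against 13). This rests on inpatients as the 60% reference, a two-sided 0.05 level and an unadjusted pooled test. The 85.0% for 3 days does not follow from the printed inputs, which give 87.1%; the gap of 2.1 points is conservative.

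A reader might infer more than the documents support:

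- **That the 80% figure is an arithmetic error.** It reproduces for an increase.
- **That the reference arm is undefined.** Section 6.4 does not label it, but objective 2.1.1 and section 6.3.1 make inpatients the natural reading.
- **That 85.0% is proven wrong.** An SD near 10.3 printed as 10 would explain it, though that is an assumption.
- **That the study is materially underpowered or its sample size must change.** The size is set by the available patients, and half a point of detectable difference is small beside the approximations in the inputs.

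**What to change.** Two edits to section 6.4:

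1. Limit the claim of more than 80% power to an increase in bacteremia with outpatient management, or report both figures: about 81% for 60% to 73% and about 77% for 60% to 47%, two-sided 0.05, with 60% as the inpatient rate. If the authors used another test or reference arm, they should recompute and print both directions on that basis.
2. Restate the 85.0% for a 3-day difference as about 87%, or print the unrounded inputs that produce 85.0%.

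The cost is a few words. The bacteremia figure for a decrease becomes slightly less favourable; the time figure, if restated, slightly more so. No patients, data or analyses are added.

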7 SAFETY MANAGEMENT

7.1 Clinical Adverse Events

As this is a medical record review, there is no possibility of a clinical adverse event (AEs).

7.2 Adverse Event Reporting

Since the study procedures are not greater than minimal risk, SAEs are not expected. If any unanticipated problems related to the research involving risks to subjects or others happen during the course of this study (including SAEs) these will be reported to the IRB in accordance with CHOP IRB SOP 408: Unanticipated Problems Involving Risks to Subjects. AEs that are not serious but that are notable and could involve risks to subjects will be summarized in narrative or other format and submitted to the IRB at the time of continuing review.

8 STUDY ADMINISTRATION

8.1 Data Collection and Management

Medical record data will be abstracted directly into electronic case report forms via REDCapTM, a secure, web-based application designed exclusively to support data capture for research studies. We will utilize REDCapTM, automated export processes to seamlessly

download the chart abstraction data to statistical packages for review and analysis. All statistical output and generated data files, tables and figures will be stored in password protected files on a secure server, which is automatically backed up each night. A unique study identification number will be assigned to participants so that no study file contains identifiable information. Each site will maintain their own master list linking each patient's unique study identification number to their medical record number. These site master lists will be stored in password-protected files that are only accessible by approved local study personnel. Identifiers will be destroyed after publication. Access to identifiable information by investigators, programmers, analyst, and statisticians will be kept to the minimum necessary mandated by HIPAA regulations. Coded, limited data sets will be shared with participating sites upon approved request, as specified in Section 8.2. Only aggregate level data will be shared with the study sponsor PCORI.

8.1.1 Data sources

Patients' electronic medical records will be queried for demographic information, clinical information, and hospital admission/discharge dates. The complete list of variables is detailed in Section 5.1.1.

8.2 Confidentiality

All data and records generated during this study will be kept confidential in accordance with Institutional policies and HIPAA on subject privacy. The Investigator and other site personnel will not use such data and records for any purpose other than conducting the study. No identifiable data will be used for future study without first obtaining IRB approval. The investigator will obtain a data use agreement between provider (the PI) and any recipient researchers (including others at CHOP) before sharing a limited dataset (dates and zip codes). Safeguards to protect confidentiality were described in Section 8.1 and are also detailed in Section 8.3.2.

8.3 Regulatory and Ethical Considerations

8.3.1 Data and Safety Monitoring Plan

Given the types of data and the observational study design, specifically the absence of an imposed intervention, there will be no Data and Safety Monitoring Board associated with this study. However, if any risks are identified, the Principal Investigator will notify the IRB promptly.

8.3.2 Risk Assessment

This is a minimal risk study. There are no new patient interventions or treatments associated with the work outlined in this proposal. As such, there are no expected additional health risks that a patient would incur as a result of participation in this study. The medical care of subjects will not be affected in any way by their participation in this study.

An unlikely but possible risk is the loss of confidentiality. We will institute strict procedures to maintain confidentiality. Each site will maintain their own master list linking each patient's unique study identification number to their medical record number. These site master lists will be stored in password-protected files that are only accessible by approved

local study personnel. Identifiers will be destroyed after publication. Entry to the offices is controlled at a main entrance by identification card readers. Research materials will be accessible only to members of the investigative team. Access to identifiable information by investigators, programmers, analyst, and statisticians will be kept to the minimum necessary mandated by HIPAA regulations to carry out the proposed research. Any publications or presentations resulting from this work will not identify participants by name, but will only present aggregate data. Our prior research employing similar precautions has demonstrated that these techniques are very successful in assuring the protection of subjects.

8.3.3 Potential Benefits of Study Participation

The patients involved in the study might not benefit directly. Results from the study may be applied in the future to AML/MDS patients in making decisions about the best way to manage neutropenia. Improved understanding of the outcomes of outpatient versus inpatient management of neutropenia will be of great importance to AML/MDS patients and the providers who care for them.

8.3.4 Risk-Benefit Assessment

This is an analysis of data that are documented in the course of providing clinical care to subjects. There are no additional interventions necessary for the execution of this study and thus there is minimal risk involved with respect to the knowledge that may result from the research.

8.4 Recruitment Strategy

No advertising will be done for this study. Local study investigators (pediatric oncologists and study coordinators) will review their hospital's AML registry to identify newly diagnosed AML and MDS patients in the retrospective period of the study. For the prospective component, local study investigators will identify newly diagnosed AML/MDS patients from weekly communications with the local inpatient leukemia service.

8.5 Informed Consent/Assent and HIPAA Authorization

8.5.1 Waiver of Consent

A full waiver of consent will be requested from the Institutional Review Board. This is an observational study and therefore complete capture of all events is ideal to ensure accurate and unbiased results. It would be impracticable to obtain consent from all eligible patients as it would require obtaining consent from parents of critically ill children, some of whom would certainly refuse to participate in a research study. Some of the patients may no longer be followed at the given institution, or may have moved out of the area, thus up-to-date contact information may not be available. Each site will submit for a waiver of consent at their respective institutions.

For those sites that do not enter into a cooperative agreement with the CHOP IRB, and a waiver of consent is not granted for prospective data collection, parents will then be given a thorough explanation of the study including the purpose, risks and benefits of participation, confidentiality, and contact information for study personnel. Families will be informed their medical care at that healthcare facility will not be affected if they choose not to participate in

the proposed research. Any site-required informed consent/assent and HIPAA Authorization will take place in a quiet, private space to ensure confidentiality, the family will be provided ample time to make an informed and thoughtful decision, and the signed document will be maintained at the local site in a secure location.

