3.3.2 Total Number of Study Sites/Total Number of Subjects Projected

Chart abstraction will be conducted at the following seventeen US investigative sites: Ann Arbor (*C.S. Mott Children's Hospital*), Atlanta (*Children's Healthcare of Atlanta*), Chicago (*Ann & Robert H Lurie Children's Hospital of Chicago*), Dallas (*Children's Medical Center of Dallas – University of Texas Southwestern Medical Center*), Detroit (*Children's Hospital of Michigan*), Houston (*Texas Children's Hospital*), Jackson (*Children's of Mississippi*), Little Rock (*Arkansas Children's Hospital*), New Orleans (*Ochsner Medical Center for Children*), Palo Alto (*Lucile Packard Children's Hospital Stanford*), Philadelphia (*Children's Hospital of Philadelphia*), Salt Lake City (*Primary Children's Medical Center*), San Diego (*Rady Children's Hospital*), Seattle (*Seattle Children's Hospital*), Denver (*Children's Hospital of Colorado*), Nemours/A.I. duPont Hospital for Children, and DFCI/Boston Children's Hospital (*Boston, MA*). These sites were chosen based on geographic location, their substantial AML/MDS patient volume, and the variation in primary strategy of neutropenia management (inpatient versus outpatient).

We expect to identify a total of approximately 600 newly diagnosed AML patients across the seventeen participating institutions over the study period of which approximately 540 are expected to meet early discharge eligibility criteria.

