8.5.2 Waiver of Assent

A full waiver of assent will be requested to collect the electronic health record of subjects. This is an observational study and therefore it is necessary to include all patients to ensure accurate and unbiased estimates.

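### The plan assumes complete capture but allows prospective enrolment by parental consent at some sites, with no record of which patients came that way and no analysis that sets them apart

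*Combined protocol and SAP*

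**What the plan says.** Section 6.4 (Sample Size and Power) starts from full capture: "Assuming 100% capture of eligible patients (waivers of consent obtained from all participating sites"). From 600 identified patients it takes 90% as early-discharge eligible. That gives 540, split into 146 outpatient and 394 inpatient, with more than 80% power for a 13-point difference from a 60% bacteremia risk.

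Section 8.5.1 (Waiver of Consent) asks for a full waiver. It calls complete capture ideal for unbiased results, and it argues that seeking consent is impracticable because it would mean approaching parents of "critically ill children, some of whom would certainly refuse to participate in a research study". Section 8.5.2, on assent, is firmer: "it is necessary to include all patients to ensure accurate and unbiased estimates".

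The second paragraph of 8.5.1 provides a fallback for a site with no cooperative agreement with the coordinating-centre IRB: when "a waiver of consent is not granted for prospective data collection, parents will then be given a thorough explanation of the study". They are told that the child's care "will not be affected if they choose not to participate in" the research.

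Section 3.3.2 says that sites were chosen partly for "the variation in primary strategy of neutropenia management (inpatient versus outpatient").

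Section 6.2 deals with confounding and exposure misclassification. Its one sensitivity analysis changes the discharge-day threshold. Section 6.3.1 (Analysis of Primary Outcomes of Interest) describes one analysis, adjusted by propensity-score quintiles.

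**The concern.** By the protocol's own account, some families who are asked will refuse. Under the fallback, a consent-route site contributes only the prospective patients whose families agree, while every other record comes from complete capture. The plan does not distinguish the two kinds of record.

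This matters for two reasons. First, selection by consent biases a comparison when it is related to the outcome, and a propensity score does not repair that: it balances measured covariates among enrolled children and cannot recover those never enrolled. Second, management strategy varies by site, so losses at a few sites need not be shared evenly between the arms. The bias could make outpatient management look better or worse, depending on which strategy those sites use. Both primary outcomes, bacteremia and time to next course, are exposed.

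As the plan stands, the team could not tell afterwards whether this had happened. Consent route is not abstracted. The data kept on screened patients (5.1.1) document ineligibility and include neither management strategy nor outcome.

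**Working it through.** **Step 1. Reproduce the plan's figures (6.4).** 600 × 0.90 = 540; 540 × 0.27 = 145.8; 540 × 0.73 = 394.2. These match.

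Bacteremia power, two-sided 0.05, pooled variance, 60% versus 73%:
- Pooled risk = (146 × 0.73 + 394 × 0.60)/540 = 342.98/540 = 0.635.
- Null standard error = √[0.635 × 0.365 × (1/146 + 1/394)] = 0.0466.
- Alternative standard error = √[0.73 × 0.27/146 + 0.60 × 0.40/394] = 0.0443.
- Power = Φ[(0.13 − 1.96 × 0.0466)/0.0443] = Φ(0.872) = 80.8%.

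This agrees with the plan's figure of more than 80%. Section 6.4 does not give the direction of the difference. A fall to 47% gives 77.2%, so the stated figure corresponds to a rise.

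**Step 2. Power with less than full capture.** Same formula, with the 27:73 split kept:

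| Patients | Power, 60% versus 73% |
|---|---|
| 540 | 80.8% |
| 530 | 80.0% |
| 520 | 79.3% |
| 502 | 77.8% |

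**Step 3. Size of a selection effect.** The documents give neither the number of consent-route sites nor the refusal rate, nor any link between refusal and outcome. The following are assumptions:
- 3 of 17 sites, of equal size, use the consent route, and 40% of their patients are prospective: 540 × 3/17 × 0.40 ≈ 38 patients.
- All 38 fall in one arm. Their share g of that arm is 38/146 = 0.260 if outpatient, or 38/394 = 0.096 if inpatient.
- Consent probability is c0 = 0.90 without bacteremia and c1 = 0.70 or 0.80 with it.
- True risk is 60% in both arms (the baseline in 6.4).

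Observed risk in the affected arm = [(1 − g) × 0.60 + g × 0.60 × c1] / [(1 − g) + g × (0.60 × c1 + 0.40 × c0)].

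| Affected arm | c1 | Calculation | Observed risk | Shift (points) | Risk ratio, outpatient/inpatient (true 1.00) |
|---|---|---|---|---|---|
| Outpatient | 0.70 | 0.5532/0.9427 | 58.7% | −1.3 | 0.98 |
| Outpatient | 0.80 | 0.5688/0.9584 | 59.3% | −0.7 | 0.99 |
| Inpatient | 0.70 | 0.5826/0.9788 | 59.5% | −0.5 | 1.01 |
| Inpatient | 0.80 | 0.5884/0.9846 | 59.8% | −0.2 | 1.00 |

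With c1 = c0 = 0.90 the shift is exactly zero, whatever the share.

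**Step 4. A harsher assumption, for scale.** If consent-route records were half of one arm and consent were 90% without but 50% with bacteremia, that arm would read 54.2%. The risk ratio would be 0.90 or 1.11, and a true null would be rejected about 21% of the time. Nothing in the documents suggests such values. At the 40% prospective share used in Step 3, half of an arm could not be reached even if every site in it used the consent route.

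**The case against.** The trigger is narrow. A site must have no cooperative agreement with the coordinating-centre IRB, must be without a waiver, and must be collecting prospective data. The documents do not say that any site meets all three conditions, so the number may be zero. This stands, and it is why the point is conditional.

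A reader might infer that consent is sought after the bacteremia window, so that children who die or leave first are never counted. The documents do not say so. Sections 4.1.2 and 8.4 have sites identify newly diagnosed patients through weekly contact with the inpatient service, which suggests an approach before the window opens three days after chemotherapy. Consent timing is not stated, so late consent is possible, but it is the worst case and not the plan. The eligibility rule in 3.4 (no fever, infection or ICU care within three days either side of the last dose) also removes some illness-related refusal before the comparison starts.

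A reader might also infer that the stated power is wrong. It is not: 6.4 makes it openly conditional on full capture, and losing a few patients from an approximate projection changes little.

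Finally, removing consent-route records from the primary analysis would lose precision and leave those sites with retrospective records only. That objection is fair, and it favours a sensitivity analysis over a redefined primary set.

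What remains is that the plan provides for refusable consent, expects refusals, and has no way of seeing their effect.

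**Conclusion.** The point holds as a conditional exposure to selection bias. The capture assumption in 6.4 and the fallback in 8.5.1 do not fit together, and neither the abstracted data nor the planned analyses address the difference. That the records are pooled is inferred from the absence of any text separating them.

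Bias requires that at least one consent-route site exists and that consent is related to outcome. On the assumptions of Step 3 it is about 0.2-1.3 points on one arm's bacteremia risk, against a 13-point target, and sites that use both strategies would dilute it. No size was worked out for time to next course.

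The stronger reading, that one arm will be made to look safer by a material amount, is not supported: the direction depends on which strategy the affected sites use, and the moderate scenario is small. This is a cheap improvement to the plan and does not invalidate the design.

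**What to change.** 1. **REDCap and 5.1.1.** Add a field for waiver versus consent route and, where consent is used, the consent date relative to the end of the course.
2. **Section 6.3.1 (primary outcomes).** Keep all records in the primary analysis. Prespecify a sensitivity analysis of both primary outcomes restricted to complete-capture records: all retrospective records, plus prospective records collected under a waiver. Membership then depends on IRB status and period, not on a child's course.
3. **Section 6.4.** Say that 540 patients and power above 80% are maxima under full capture, and give power at lower capture for 60% versus 73%: 80.8% at 540, about 79% at 520, about 78% at 502.

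The cost is one extra REDCap entry, one extra analysis and a slightly less favourable power statement. The restricted analysis is less precise: without the 38 patients of Step 3, the Step 1 formula gives about 78% power if they come evenly from both arms (502 patients), about 80% if all are inpatient (146 and 356), and about 71% if all are outpatient (108 and 394). That is acceptable for a sensitivity analysis. Because consent-route sites would keep only retrospective records in it, a difference from the primary result should be read with that period imbalance in mind. If no site uses the consent route, the restricted analysis is the primary analysis and nothing is lost.
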